All of these measures will be collected at baseline and post-intervention.

Aim 3 will address our second objective to assess the acceptability, appropriateness, and feasibility of critical narrative development as an intervention strategy for SGM EA of color. We will conduct in-depth interviews with participants after completing the CNI (photo-novella or digital storytelling), which will assess the participants' acceptability of the critical narrative intervention. Utilizing a semi-structured interview protocol, participants will be asked questions about their experience with the intervention, including how it impacted the participant. Some sample question includes, "Tell me about your experience with creating your narrative," "What did you like (and not like) about this process," and "How has this project impacted you?"

We will also assess the acceptability, appropriateness, and feasibility of CNs for SGM EA of color utilizing several validated measures after participants complete their CN:

- 1) the acceptability of intervention measure (AIM) to assess the acceptability,
- 2) the intervention appropriateness measure (IAM) to assess the appropriateness, and
- 3) the feasibility intervention measure (FIM) to assess feasibility.

BACKGROUND:

The transition into adulthood for sexual and gender minority (SGM) emerging adults (EA; ages 18-24) in the United States, along with stressors of stigma experiences as a sexual minority and/or gender minority, may contribute to the disproportionate mental illness risk (e.g., depression, suicidal ideation, anxiety, and substance use) and decreased mental health treatment compared to their peers (Swann et al., 2020; Tan et al., 2017). These mental health differences are especially pronounced in SGM EA of color (racial/ethnic minorities; Mereish et al., 2021).

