Ads will link interested individuals to the study's eligibility screener to verify their eligibility. We have recruited through these platforms for over a decade with a significant track record of demonstrated success. We plan to use lessons learned from these efforts to guide the implementation of our proposed recruitment strategy.

If necessary, we will leverage our connections in the national LGBTQ+ community and conduct in-person or e-mail recruitment and word-of-mouth referrals. We will also hang flyers in local areas including on campus, businesses, and public spaces (as allowed).

The eligibility screener will be a REDCap survey that asks participants to fill out demographic information related to inclusion and exclusion criteria. The eligibility screener will also ask participants to provide contact information (Name, phone number, email address, preferred contact method, and time of day available for contact) for a study member to reach out to them if they are eligible and to schedule a baseline visit. The screener will also ask for participants to provide their longitude and latitude to be eligible for the study. This information will be used to confirm that they are eligible and live within the United States.

5. Early Withdrawal of Subjects:

Retention during a longitudinal study is expected to be 80% or greater. Participation in the study is voluntary; therefore, a participant may withdraw from the study at any time by communicating with the study team via phone or email. The research team member will work to communicate and keep in touch with participants throughout the study. However, if the research team member is unable to reach a participant after extensive attempts or the participant fails to attend follow-up visits, the participant may be withdrawn from the study.

6. Vulnerable Populations:

This research study does not include children, pregnant women, fetuses, neonates, or prisoners.

7. Populations vulnerable to undue influence or coercion:

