
Potential participants interested in participating in the study will first complete an eligibility screener. Those participants that are deemed eligible based on inclusion/exclusion criteria will be contacted by a study team member to schedule a virtual baseline visit.

Participants will complete 2 online surveys during the study: at baseline and after completion of the critical narrative development (about 1 month after initial enlistment into the study). Assessments will take 20-25 minutes to complete. The primary goal of the two surveys will be to assess the preliminary effectiveness of the critical narratives at impacting depression, anxiety, self-esteem, psychological well-being, and empowerment. All surveys will be housed and implemented through REDCap. Below is a table of the measures utilized in the surveys.

Construct	Measure	Description	Citation	Time Point	
				Baseline	1-Month
Depression Symptoms	Patient Health Questionnaire (PHQ-9)	The PHQ-9 is a 9-item depression symptom checklist scored from 0 to 3 on a Likert scale of "not at all" to "nearly every day." The PHQ-9 has demonstrated high internal reliability ($\alpha = .88$) and test-retest reliability ($\alpha = .94$)	Kroenke, K., Spitzer, R.L., & Williams, J.B. (2001). The PHQ-9: Validity of a brief depression severity measure. Journal of General Internal Medicine , 16(9), 606-613.	X	X
Anxiety Symptoms	Generalized Anxiety Disorder (GAD-7)	The GAD-7 is a 7-item measure designed to assess anxiety symptoms scored from 0 to 3 on a Likert scale of "not at all" to "nearly every day," with total scores ranging from 0 to 21. The	Spitzer, R.L., Kroenke, K., Williams, J.B., & Lowe, B. (2006). A brief measure for assessing generalized anxiety disorder: the GAD-7.	X	X

		GAD-7 is valid with intercorrelations with the PHQ-2 ($r = .64$) and the Rosenberg Self-Esteem Scale ($r = .43$) and has good reliability ($\alpha = 0.89$; Lowe et al., 2008).	Archives of internal medicine, 166 (10), 1092-1097.		

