Digital Story: Participants in the digital storytelling intervention will be asked to tell their story in 3-6 minutes (two videos total, 1-3 minutes each) utilizing a video format which can include still or moving images, sound, music, and voiceover. Participants will be provided with a guide on software or applications that they can use to create their stories. Participants will be provided with a manual or basic guide to digital stories for their reference. Participants

will be provided with guidance on expectations of the video, including format, length, quality, and closed captions for accessibility.

At the baseline visit after the survey and interview, participants will be randomized into one of the two intervention conditions (photo-novella or digital story). Once the participant is randomized, they will be provided with the electronic manual (based on their intervention). The research team member will provide guidance on what to expect (i.e., how many photos to take and what the prompt is) and go over the manual with the participant. The participant will then be given the opportunity to ask questions.

The participants will be given one month to complete their narrative and be asked to digitally submit their work to the research team during the 1-month visit. Participants will also be given the opportunity to present their work at a gallery (but not required to), which will be scheduled later (about ten months from the date of the first enrollment). The gallery and participation in the gallery are entirely voluntary and will not affect participation in the study.

A week before the scheduled 1-month follow-up, a research team member will reach out to the participant to confirm the 1-month study visit via phone, e-mail, or text as indicated in the participant's preferred contact method. A research team member will reach out every two days for confirmation until received from the participant.

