Participants will receive a link via email a day before their one-month follow-up visit to complete a follow-up survey (15-20 mins). During the one-month follow-up, a research team member virtually on Zoom will conduct a follow-up interview (45-60 mins) asking participants about their experience of creating their critical narrative piece. At the one-month follow-up, research team members will review the final critical narratives of the participants digitally. Two days before the one-month follow-up, participants will receive a link via email to a Box folder (that is HIPAA compliant) where they can upload their photos/videos.

The participants will be notified of the gallery date and invited to attend. The gallery is optional and does not impact participation in the study.

Use of Deception:

Not applicable. This study does not utilize deception.

Statistical Analysis:

Prior to conducting our multivariate analyses, we will examine study variables using descriptive statistics and test for differences across demographic characteristics (e.g., race/ethnicity, age, education) using t-tests, ANOVAs, and Chi-squares, as appropriate. As participants will be randomized to the two groups, systematic baseline differences are not expected; however, if some parameters differ across conditions at baseline, they will be included as covariates in subsequent multivariate models.

As appropriate, we will compare differences from baseline to the 1-month outcomes across our outcome measures using t-tests and Chi-squares. We will also estimate the effect size of our interventions to aid us in determining the future sample size needed for a larger study on the intervention.

Power analysis

Due to the exploratory nature of this study, a power analysis was not conducted for an a priori sample size. However, we will be conducting in-depth interviews until we reach saturation. Typical saturation for in-depth interviews is determined as between 9-17 participants (Hennink & Kaiser, 2022), therefore, we will recruit a total of 30 participants (15 participants for each condition).

RISK/BENEFIT ASSESSMENT:

1. Risks:

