We will implement several strategies to offset the risks of loss of confidentiality related to data collection. To minimize the risk of participants feeling uncomfortable about answering personal questions, we will use self-completed online surveys for many of our assessments. Participants will input the answer to the question themselves and will be able to refuse to answer any question that makes them uncomfortable on either the self-report assessments or the in-depth interview. In interviews, participants will not be named and any additional reference to people and/or locations will be masked to increase their privacy. Once audio recordings of interviews have been transcribed and de-identified, they will be destroyed to prevent any audible identification of participants.

5. Protected Health Information

Participant-protected health information (PHI) will be collected, including Name, Telephone Number, IP address, and Electronic Mail address, for contacting participants throughout the study, including follow-up reminders. PHI of participants' date of birth will be utilized to determine age for eligibility (inclusion). Participants will also be audio recorded during their interviews. All interviews, after being transcribed and de-identified, will be destroyed.

6. Compensation:

Our incentive schedule will encourage assessment and interview completion, increasing the rates to encourage the completion of future study visits.

- At baseline for the completion of the survey and interview, participants will receive \$30.
 - To confirm eligibility at baseline, longitudinal and latitude data will be collected and required to receive compensation at baseline.
- At one month for the completion of the narrative, survey, and interview, participants will receive \$45.

Participants will be paid virtually using Greenphire Virtual Clincards; therefore, we will collect emails from each participant.

7. Data and Safety Monitoring:

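### The protocol ties the $45 one-month payment to narrative, survey and interview together with no part payment, so participants who do not finish the narrative may have less reason to give follow-up data

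*Combined protocol and SAP*

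**What the plan says.** Under Risk/Benefit Assessment, 6. Compensation, the stated aim is: "Our incentive schedule will encourage assessment and interview completion, increasing the rates to encourage the completion of future study visits". The narrative is not named in that aim. Two payments follow. The first is "At baseline for the completion of the survey and interview, participants will receive \$30". The second is "At one month for the completion of the narrative, survey, and interview, participants will receive \$45". No amount is given per component, and no rule covers a participant who completes some of the three items but not all.

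Other sections bear on how the 1-month data are obtained:

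- Methods, 1. Study Instruments, times the two surveys "at baseline and after completion of the critical narrative development (about 1 month after initial enlistment into the study".
- The Aim 3 text under Objectives (Outcomes) collects the acceptability, appropriateness and feasibility scales "utilizing several validated measures after participants complete their CN", and holds the exit interviews once the intervention is complete.
- Study Procedures, Detailed Description, says that participants will "be asked to digitally submit their work to the research team during the 1-month visit". It also says: "Participants will receive a link via email a day before their one-month follow-up visit to complete a follow-up survey (15-20 mins". Neither sentence makes the survey depend on the narrative.
- Subject Follow-up describes the 1-month visit as interview, survey and final submission together, with contact every two days until the visit is confirmed.
- Early Withdrawal of Subjects expects retention of 80% or more and provides that if "the participant fails to attend follow-up visits, the participant may be withdrawn from the study".

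**The concern.** At baseline, payment follows data collection. At one month, an intervention product joins the same condition. The product takes real work: 12 captioned photographs in one arm, two captioned videos in the other. Everyone enrolled has a PHQ-9 score of at least 10, and the Subject Privacy section itself names distress while creating the narrative as a risk. Some participants may reach one month without a finished piece. The protocol text offers them no stated payment for the PHQ-9, GAD-7, well-being, self-esteem and empowerment measures, for the acceptability scales, or for the exit interview.

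Two things are at stake. For Aim 2, outcome data could be missing in a way that is related to adherence, and possibly unevenly between arms because the two tasks differ. For Aim 3, the people who found the task hard or unsuitable are those whose views the acceptability assessment most needs. The Statistical Analysis section states no missing-data method and no analysis set, so nothing later in the plan addresses such a pattern.

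**Working it through.** **Does the rest of the plan supply the missing rule?** The sections can be set side by side.

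1. Stated purpose (Compensation): assessments and interviews. Baseline condition: survey and interview, which matches. One-month condition: narrative, survey and interview, which is wider than the purpose.
2. The same section uses payment conditionally elsewhere: location data are required before the baseline sum is paid. Staff could reasonably read the 1-month sentence as a condition too.
3. The survey link and the reminders go out without reference to the narrative. That settles delivery of the survey, not payment for it.
4. Study Instruments and the Aim 3 text place the follow-up measures after narrative completion. No section says that a participant without a narrative is still asked to attend.

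So the protocol text contains no payment rule for follow-up without a narrative.

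**Scale of a possible effect.** The plan has no figure of its own to reproduce here, beyond 15 + 15 = 30 randomised. At the retention floor, 0.80 × 30 = 24 are observed and 30 − 24 = 6 are missing. The documents do not say how many of those 6 would lack a narrative, or how many would be lost because of payment.

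Let *m* be the fraction missing, and *g* the mean change in observed participants minus that in missing participants, in SD units. The mean over all randomised is (1 − *m*) × observed mean + *m* × missing mean. The observed mean therefore differs from it by *m* × *g*. All values of *g* below are assumptions, and *g* may take either sign.

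| *m* | *g* = 0 | *g* = 0.25 | *g* = 0.5 | *g* = 1.0 |
|---|---|---|---|---|
| 0.10 | 0 | 0.025 | 0.05 | 0.10 |
| 0.20 | 0 | 0.05 | 0.10 | 0.20 |

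Between arms, with the same *g* in both, the bias is the difference in loss fractions times *g*. For six losses and *g* = 0.5:

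- split 3/3: 0
- split 2/4: (4/15 − 2/15) × 0.5 = 0.07 SD
- split 0/6: (6/15) × 0.5 = 0.20 SD

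For comparison, the half-width of a 95% confidence interval for the between-arm difference is about 0.85 SD with 12 per arm, from t(0.975, 22 df) × √(1/12 + 1/12). For Aim 2 the illustrative bias is well inside sampling error.

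**What the change could recover.** Starting from 6 missing, if none, half or all of the losses were due to payment, then 24, 27 or 30 are observed. At *g* = 0.5 the bias in mean change goes from 0.10 to 0.05 to 0 SD (0.20, 0.10 and 0 missing, each times 0.5).

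**The case against.** The strongest reply is that the sentence simply lists what happens at the 1-month visit. Subject Follow-up names the same three items as the content of that visit, and the purpose sentence in Compensation ends on completing future visits. On that reading the $45 is a visit payment and nobody would be refused it. The visit is booked at baseline, reminders continue until it is confirmed, and the survey link is sent regardless of the narrative. A part-payment rule may also sit in the consent form, whose text is not in the public document. This much stands: the all-or-nothing reading is possible but not certain, and the point is limited to what the protocol states. That two readings are open is itself a reason to settle the wording.

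A reader might go further and infer three things that the documents do not support:

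- *That outcome data will go missing because of non-adherence.* No text bars a participant without a narrative from the survey, the interview or payment, and no figure says how many losses payment would cause.
- *That results will be biased upward.* This needs the missing participants to improve less than those observed. Everyone enters above a PHQ-9 threshold, so some improvement may occur with no narrative at all, and the gap could be zero.
- *That failing to submit a narrative leads to withdrawal.* Early Withdrawal lists loss of contact and missed visits, not non-submission.

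**Conclusion.** The point holds as a design weakness that is cheap to remove. The protocol ties the only 1-month payment to the narrative as well as to the data, against the section's own purpose, and states no part payment. Participants who do not finish may therefore have less incentive to give Aim 2 outcomes and the exit interview, and missing data could then be related to adherence.

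Size and direction are unknown. The 0.05 to 0.20 SD range assumes 20% loss and a gap of 0.25 to 1.0 SD between observed and missing participants, and the effect is zero if there is no gap. The 20% is the complement of an expected retention floor, not a rate of unfinished narratives. For Aim 3 the worry is who is missing more than how many: 24 interviews would still exceed the 9 to 17 that the Power analysis section cites for saturation, but they could under-represent those who did not finish.

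**What to change.** 1. In Compensation, keep the $45 maximum. State that payment for the 1-month survey and interview is made whether or not a narrative is submitted. If the sponsor wishes to reward the narrative, make that a separate, smaller part of the same total.
2. Say in the visit reminders, and in the consent form if it does not already do so, that follow-up is sought and paid for even if the narrative is unfinished.
3. Align the wording in Study Instruments and in the Aim 3 text under Objectives, so that the survey, scales and interview fall due at one month for everyone randomised. Changing the payment alone would leave those passages implying that only completers are followed.
4. Report 1-month data completeness by narrative completion and by arm, so that any pattern is visible.

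The cost is about one sentence in Compensation, small matching edits elsewhere and no increase in the maximum paid per person. The downside is a somewhat weaker incentive to finish the narrative, of unknown size; keeping a separate narrative part would limit it.

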Photo-novella, or the use of photographs to tell a story, has been used as a group intervention (photovoice) and as an individual narrative intervention. Photographs as a voice or narrative have been found in a recent systematic review to be effective in participant empowerment, community change, knowledge acquisition, and reaching policymakers.

Digital Stories visually represent first-person narratives that utilize present-day digital culture. Digital stories ask participants to tell a story by creating a short (3-minute) autobiographical vignette synthesizing written text, still and moving imagery, voice, and sound. Digital stories include multiple sensory contexts (e.g., text, spatial, visual, verbal,

and gestures) to convey meaning and can be interpreted on different levels by storytellers and listeners. In a review of digital stories for health promotion, digital stories were found to improve confidence, motivation, behavior change, and/or social change.

At the end of the pilot study, we will provide a voluntary space as a gallery for the critical narratives to be displayed and open to the public. The gallery will be optional for participants who wish to display their critical narratives.

OBJECTIVES:

Our primary objective is to identify the potential use of critical narratives as an elicitation strategy to increase empowerment (e.g., increase in self-esteem), and improve mental health symptoms (e.g., decrease in depression and anxiety, and increase in psychological well-being) in vulnerable populations of SGM individuals of color living with depression. Our secondary objective is to assess the feasibility, acceptability, and appropriateness of critical narratives (photo-novella and digital storytelling) for SGM EA of color. Our specific aims are:

1. Examine the experiences of discrimination and acceptance of SGM EA of color living with depression in their community,
2. Evaluate the impact of CN on empowerment (e.g., self-esteem) and mental health outcomes (depression, anxiety, and psychological well-being) of SGM individuals of color.
3. Understand the acceptability, appropriateness, and feasibility of critical narrative development as a strategy for SGM EA of color.

Outcomes

The study has two primary outcomes addressed in Aim 1 and Aim 2.

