Participants provide consent for the research team to retain email addresses and phone numbers for participant follow-up. During the baseline visit, participants will be scheduled for a 1-month follow-up visit, including an interview, survey, and final submission of the critical narrative. A week before the scheduled 1-month follow-up, a research team member will reach out to the participant to confirm the 1-month study visit via phone, e-mail, or text as indicated in the participant's preferred contact method. A research team member will reach out every two days for confirmation until received from the participant. This will aid in ensuring confirmation of the scheduled follow-up and retention of participants at the follow-up time point.

STUDY PROCEDURES:

Detailed Description:

The research activities involve a two-arm pilot enrolling a sample of 30 participants who identify as SGM, POC, and living with moderate to severe depression. After consent and completion of the baseline survey (15-20 min) and interview (45-60 min), participants will be randomized into one of two critical narrative interventions: photo-novella (n=15) or digital storytelling (n=15).

All participants will be given the same two prompts for their narrative intervention asking, "Share an experience of when you have felt seen as an SGM Person of Color." AND "share an experience of when you have felt unseen as an SGM person of color."

Photo-Novella: Participants in the photo-novella intervention will be asked to tell their story through 12 photographs and a caption (6 for the first prompt and 6 for the second prompt). Participants will be instructed to take a photograph answering the two prompts. Participants may use their smartphones or digital camera to capture their photographs. Participants may also edit their photographs using photo-editing software for aesthetics. Participants will also be asked to provide a short caption (no more than two sentences) explaining their photograph and provide a title for their work. Participants will be provided with a basic guide on photography and how to "snap a picture."

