- Prior to access to any study-related information, personnel will be required to sign statements agreeing to protect the security and confidentiality of identifiable information.
- Whenever feasible, identifiers will be removed from study-related information.
- A Certificate of Confidentiality will be obtained, because the research could place the subject at risk of criminal or civil liability or cause damage to the subject's financial standing, employability, or liability.

A waiver of documentation of consent is being requested, because the only link between the subject and the study would be the consent document and the primary risk is a breach of confidentiality. (This is not an option for FDA-regulated research.)

Precautions are in place to ensure the data is secure by using passwords and encryption, because the research involves web-based surveys.

Audio and/or video recordings will be transcribed and then destroyed to eliminate audible identification of subjects.

Other (specify):

Data will be kept for five years after the completion of the study (de-identified). Photos/videos of the narratives from participants will be kept for five years after the completion of the study. If participants choose to participate in the optional gallery after study completion, photos/videos will then be kept indefinitely. Please note that the gallery is an artistic endeavor and not an extension of the research (e.g., no data will be collected during/about the gallery).

Data from participants who fill out the eligibility survey – but are not eligible/do not enroll in the study will be kept within REDCap (HIPAA compliant survey application) until the completion of the study. Once the study has been completed, this data will then be deleted.

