The Principal Investigators will provide oversight of all study procedures and quality assurance checks. We have several mechanisms to ensure the security and integrity of the data. The intervention content, questionnaires, and personal information will be secured with role-based security that will provide different types of users with different access privileges. All printed records pertaining to the study containing collected data will be securely stored by the Principal Investigators in a locked metal file cabinet housed in the Department of Family and Community Health. No names or other identifying information appear on data documents or in data files, as the re-contact information will be stored separately. Electronic files and records will be stored in a firewalled, encrypted server at the University of Pennsylvania; only research staff will have access to this directory.

All staff will complete human subjects research training and data safety training as part of their project onboarding. To ensure participants' safety as well as the data's validity and integrity, only staff with extensive experience with SGM youth and

suicide prevention will be hired. All staff will have signed a confidentiality agreement. The Principal Investigators and Project Director will monitor staff closely. Staff deficient in any aspect of performance will be re-trained, closely monitored for proficiency, and if not adhering to established protocols and procedures, will be terminated. Only designated staff will have access to the data. The Principal Investigators and Co-Investigators will be responsible for disseminating study findings through presentations and publications. The Principal Investigators will also be solely responsible for handling any requests from other investigators to examine the data collected during this study.

If a participant (enrolled) or prospective participant reports suicidality or another intent to harm, we will have to break confidentiality. We will inform the participant of this verbally and within the consent form. We will note that we may need to break confidentiality for their safety if they report suicidality or other intent to harm. This may include contacting emergency contacts that they provide to us, putting them in contact with a study clinician, or calling 9-1-1 to have emergency response service be put in contact with them.

8. Investigator's Risk/Benefit Assessment:

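### The statement that data files hold no identifying information is not supported for the narrative photographs and videos or for the location coordinates

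*Combined protocol and SAP*

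**What the plan says.** Section 7, Data and Safety Monitoring, makes an unqualified statement: "No names or other identifying information appear on data documents or in data files, as the re-contact information will be stored separately". Section 4, Subject Confidentiality, adds that all participant data will be de-identified before analysis.

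**Narratives.** The introduction describes a digital story as a first-person "autobiographical vignette synthesizing written text, still and moving imagery, voice, and sound". Under Study Procedures, participants in that arm make two videos, "utilizing a video format which can include still or moving images, sound, music, and voiceover". For the other arm: "Participants in the photo-novella intervention will be asked to tell their story through 12 photographs and a caption". On retention, Subject Confidentiality says: "Photos/videos of the narratives from participants will be kept for five years after the completion of the study". For those who join the optional gallery, retention is indefinite.

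**Coordinates.** Under Subject Recruitment and Screening: "The screener will also ask for participants to provide their longitude and latitude to be eligible for the study". The Compensation section collects them again at baseline as a condition of payment. Section 5 says that protected health information "will be collected, including Name, Telephone Number, IP address, and Electronic Mail address"; it then adds date of birth and mentions interview audio.

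**Destruction.** The Data Management section lists name, e-mail address and phone number for destruction at the end of the study.

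**The concern.** Storing contact details separately removes one route to identification. It does nothing about a file whose content identifies the person, such as a voice telling a personal story, or about a location.

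The disclosure would be sensitive. The prompts ask about being seen and unseen as a sexual or gender minority person of color, and enrolment requires a PHQ-9 score of 10 or higher. A recognisable narrative held as study data can therefore reveal minority status and depression together.

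The wording also has consequences after the trial. The Consent Process section seeks approval to retain data for future research, and Data and Safety Monitoring foresees requests from other investigators to examine the data. Anyone relying on the sentence quoted above could release narratives on the footing that they carry no identifiers.

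**Working it through.** The plan gives no figure to reproduce. The check compares, for each kind of material, what is collected, what is named as an identifier, and what happens to it.

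| Material | Named in section 5 (PHI)? | Rule for destruction or retention | De-identification step described |
|---|---|---|---|
| Name, e-mail, phone | Yes | Destroyed at study end (Data Management) | Stored separately |
| Interview audio | Yes | Destroyed after transcription | People and locations masked |
| Narrative photographs | No | Five years; indefinite if in gallery | None |
| Narrative videos | No | Five years; indefinite if in gallery | None |
| Coordinates, not enrolled | No | Screener data deleted at study completion | Not needed after deletion |
| Coordinates, enrolled | No | None stated | None |

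**Step 1: are narratives data files?** The term is not defined. Data Management groups intervention data with survey data under study ID numbers, so the natural reading is that they are.

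**Step 2: does the protocol regard such content as identifying?** For interviews it does. Audio is destroyed to prevent audible identification, and references to people and places are masked. A voiceover in a retained video has the same property, yet no comparable step is described for it.

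**Step 3: does the stated reason reach this material?** No. It concerns re-contact information alone. In the retention paragraph of Subject Confidentiality, the general data are labelled as de-identified, while the next sentence, on photographs and videos, carries no such label.

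**Step 4: what are the coordinates for?** The stated use is to confirm that the person is in the United States and eligible, with baseline payment conditional on that check. A yes/no result serves this. The fraud checks described under Subject Privacy use e-mail, IP address, browser or operating system and completion time, not coordinates.

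**Step 5: size.**
- Photographs: 15 participants × 12 = 180.
- Videos: 15 participants × 2 = 30.
- At the protocol's 80% retention figure, assuming equal loss in both arms, 15 × 0.8 = 12 per arm, giving 12 × 12 = 144 photographs and 12 × 2 = 24 videos.
- Coordinates: of about 200 screened, about 200 − 30 = 170 fall under the deletion rule and 30 have no stated rule.

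These are counts of files and people. They do not say how many files would in fact identify someone.

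**The case against.** The strongest reply is that the plan does protect this material. Intervention data are coded by study ID, role-based security expressly covers intervention content, uploads go to a HIPAA-compliant folder, and files sit on an encrypted server used by staff bound by confidentiality agreements. This stands. A reader might infer that the promised protection does not exist at all, and the documents do not support that. These measures limit who sees the files; they do not make the files non-identifying, which is what the sentence asserts.

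It can also be said that the separate retention sentence shows the authors already distinguish narratives from de-identified data, and that the statistical section plans no analysis of narrative files. Both are fair. They show that the absolute sentence needs a qualification, not that it has one.

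On coordinates, the identifier list opens with the word including and may not be exhaustive, collection is disclosed openly, and the general rule that data are kept de-identified might be taken to imply removal. But the destruction list is specific, and nothing tells staff to treat coordinates as an identifier. The Consent Process section, meanwhile, speaks of retaining all screener data without giving a duration.

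Four further inferences are tempting and should not be drawn.
- **Precise location.** The precision of the coordinates is not stated.
- **Faces and other people in the images.** No section says they will appear, and none excludes them. Voiceover and images are permitted, not required.
- **A contradiction between keeping and destroying videos.** The confidentiality checklist says: "Audio and/or video recordings will be transcribed and then destroyed to eliminate audible identification of subjects". Nearly the same is said elsewhere of interview recordings, which is most likely what it means, and the available text does not show which boxes are ticked.
- **Faulty manuals or consent form.** Neither is in the documents, so nothing can be said about what they contain or omit.

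**Conclusion.** The point holds in a limited form. The unqualified statement under Data and Safety Monitoring is not supported for narrative media or for coordinates, and the promise to de-identify all data before analysis has no described method for either. The gap covers up to 180 photographs and 30 videos at full completion, and the coordinates of the 30 enrolled participants. Indefinite retention applies only to those who choose the gallery.

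The conclusion rests on two readings: that narratives count as data files, which the Data Management grouping favours but does not settle, and that a voice or personal story can identify its author, which the protocol's own handling of interviews supports. It bears on confidentiality alone and alters no outcome, estimate or sample size. It is still worth correcting, because it changes what is stored and how narratives may be shared, at little cost.

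**What to change.** 1. At each location check, record only yes or no for being in the United States and delete the raw coordinates.
2. Name coordinates and narrative photographs, video and voice as identifiers in the Protected Health Information section, and hold and share the narratives as identifiable records.
3. Qualify the sentence in Data and Safety Monitoring and the one in Subject Confidentiality on de-identification before analysis, so that both except narrative media. Then check that the consent form says the same.

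The cost is an amendment through the IRB and a small change to the REDCap location field. The one practical loss is that raw coordinates would no longer be available for a later re-check of eligibility. No planned analysis described in the protocol uses them.
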